### **HIV Power Calculations**

For HIV we focused on multiple sexual partners (more than one partner at the same time, or at least two partners in the previous year) as a primary risk factor in South Africa, and estimated that the prevalence of multiple sexual partners in the control and case populations. We assumed a 10% difference in the prevalence of multiple sexual partners between cases and controls. Depending on the prevalence of multiple sexual partners in the control population the odds ratio that we will be able to detect with 80% or higher power is between 1.65 and 1.94 for

a study with 300 cases and 900 controls (Table 8). In the Monte Carlo, simulation estimates for odds ratios were similar regardless of the ratio of cases to controls, 1:1, 1:2, or 1:3. That is, a 1:1 ratio would allow for similar odds ratios to be detected. This analysis assumes that the selection of controls from the same geographic regions as cases will be consistent with the assumptions of inter cluster correlations that were defined for the Monte Carlo simulation power analysis. However, there is substantial uncertainty around how similar the behavioural exposures of cases and controls between different clusters (clinics) will be. For this reason we believe including a larger number of controls per case may be required in order for the team to ensure the study meets its primary objectives. Recall that we will be accepting virtually all cases so the only way to enlarge the sample is to include more controls. Also, including more controls will allow for secondary analyses of behavioural prevalence in donors without infection. For example, the study is interested in understanding the range of relatively common to less common risk factors for newly acquired infections in blood donors in South Africa. We want to be able to detect and report findings across a range of behavioural exposures. It is not expected the distribution of all behaviors will conform to the assumptions made for the Monte Carlo power analysis. Risks other than multiple sexual partners will have different prevalence in the donor population and may have smaller differences in exposure prevalence between cases and controls within each clinic. For these reason we are planning to enroll cases and controls in a ratio of 1:3.

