**SECTION E - SEXUAL HISTORY**

**READ and HEARD:** Now, we want to ask about the people you have had sex with and your sexual partners. We understand that these questions are about intimate and private matters, which could make you uncomfortable. Please keep in mind that the questions are part of a scientific study, and the researchers will keep your responses confidential. Your individual responses will not be known by SANBS. Please answer these questions to the best of your knowledge and as truthfully as you can.

E1. Do you consider yourself to be? (Choose one)

- 1        Straight/heterosexual
- 2        Bisexual
- 3        Gay/homosexual
- 97       Don't Know
- 98       Refuse to Answer

**READ and HEARD:** The following questions will ask you about your sexual experiences. In these questions, include only those people you have had oral, vaginal, or anal sex with. Do not include people that you have only kissed. Please try to be as accurate and honest as possible. If you cannot remember the precise answers below, please provide your best estimates.

**Please note:** For the next few questions the terms “sexual contact” and “sex” refer to any of the following activities, whether or not a condom or other protection was used:

1. **Vaginal sex (contact between penis and vagina)**
2. **Oral sex (mouth or tongue on someone’s vagina, penis, or anus)**
3. **Anal sex (contact between penis and anus)**

E2a. (Ask of Men Only) How many different women have you had sex with since you first began having sex?

— — — —

- 9997        Don't Know
- 9998        Refuse to Answer
- 9999        Not Applicable

E2a.1 **If Answer is Don't Know, Else Skip.** If you Don't Know, can you give an approximate answer? \_\_ \_

E2b. (Ask of Men Only) How old were you when you had sex with a woman for the first time?

\_\_ \_

9997 Don't Know

9998 Refuse to Answer

9999 Not Applicable

E3a. (Ask of Men Only) How many different men have you had sex with since you first began having sex?

\_\_ \_ \_\_ \_

9997 Don't Know

9998 Refuse to Answer

9999 Not Applicable

E3a.1 **If Answer is Don't Know, Else Skip.** If you Don't Know, can you give an approximate answer? \_\_ \_

E3b. (Ask of Men Only) How old were you when you had sex with a man for the first time?

\_\_ \_

9997 Don't Know

9998 Refuse to Answer

9999 Not Applicable

E2a. (Ask of Women Only) How many different men have you had sex with since you first began having sex?

— — — —

9997 Don't Know

9998 Refuse to Answer

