**If E2a is equal to 0 and E3a is equal to 0 and B1 is equal to 1, then skip to Section H.**

**If E2a is equal to 0 and E3a is equal to 0 and B1 is equal to 2, then skip to Section H.**

E5a. Have you ever been sexually abused, sexually assaulted or forced to have any kind of sex when you did not want to?

- 0 No ***Skip to Next Section.***
- 1 Yes
- 7 Don't Know
- 8 Refuse to Answer

E5b. In the six months before your donation were you sexually abused, sexually assaulted or forced to have any kind of sex when you did not want to?

- 0 No
- 1 Yes
- 7 Don't Know
- 8 Refuse to Answer

E5c. In the six months before your donation were you sexually abused, sexually assaulted or forced to have any kind of sex when you did not want to with someone you consider to be an intimate partner, such as a spouse, husband, wife, boyfriend or girlfriend?

- 0 No
- 1 Yes
- 7 Don't Know
- 8 Refuse to Answer

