**SECTION F - SOCIAL/SEXUAL MATRIX**

**READ and HEARD:** *This next set of questions is about sexual experiences you may have had. While some people have had a lot of sexual experience, others have not, so questions may or may not apply to you. Please answer these questions as accurately as possible. Remember that answers that you provide will be combined with those from all other people who complete the questionnaire and we will never disclose individual responses to any question. Specifically, we will ask about sexual activities that include vaginal, anal and/or oral intercourse. Please answer these questions to the best of your knowledge and as truthfully as you can.*

F1. How many people did you have sex with in the 12 months before your blood donation?

— —

- 97 Don't Know
- 98 Refuse to Answer
- 99 Not Applicable

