**If F1 is equal to 0, then skip to instruction Section H.**

F2. How many people did you have sex with in the 6 months before your donation? **(THIS INFORMATION DOES NOT APPEAR TO THE RESPONDEN: This is the seed number for the social matrix (0 up to 5 partners in last six months - persons with more than 5 partners will only be asked about 5 partners).**

— —

- 97 Don't Know
- 98 Refuse to Answer
- 99 Not Applicable

**READ and HEARD:** *Now, we want to ask about the people you have had sex with and your sexual partners. If you had more than five partners in the 6 months before your blood donation, we are only going to ask you about the five most recent people you have had sex with and your sexual partners. Please start with the most recent person you had sex with before your blood donation and then move back in time.*

F3. What is Partner 1's gender?

- 1 Male
- 2 Female
- 3 Transgender
- 97 Don't Know
- 98 Refuse to Answer

F4. How old is partner 1?

— —

- 97 Don't Know
- 98 Refuse to Answer

F5. When did your relationship with partner 1 start? We recognize that you may not remember the exact date and so we are asking that you try to recall the month and the year.

Month \_\_\_\_\_ Year \_\_\_\_\_

- 97 Don't Know
- 98 Refuse to Answer
- 99 Not Applicable

F6a. Are you currently have sex with partner 1?

- 0 No
- 1 Yes
- 97 Don't Know
- 98 Refuse to Answer
- 99 Not Applicable

If F6a = yes, skip to F7

F6b When did your relationship with partner 1 end? We recognize that you may not remember the exact date and so we are asking that you try to recall the month and the year.

Month \_\_\_\_\_ Year \_\_\_\_\_

97 Don't Know

98 Refuse to Answer

99 Not Applicable

F7. What type of partner is partner 1? (Choose one)

1 Primary partner - Your husband, wife, boyfriend or girlfriend

2 Regular partner - Had sex with regularly, but not your primary partner (husband, wife, boyfriend or girlfriend)

3 Casual partner - Had sex more than once but not regularly

4 One time partner - Had sex only once

5 Anonymous partner - Did not know, met for sex, never plan to see again

6 Sex worker - Money or other goods were exchanged for sex

97 Don't Know

98 Refuse to Answer

F8. How would you describe partner 1's race or ethnicity? (Choose one)

- 1 Black
- 2 White
- 3 Coloured
- 4 Asian
- 6 Other
- 97 Don't Know
- 98 Refuse to Answer

F9. What country is partner 1 from?

- 1 South Africa
- 2 Zimbabwe
- 3 Malawi
- 4 Mozambique
- 5 Swaziland
- 6 Botswana
- 7 Lesotho

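### The recent-partner counts F1 and F2 have no approximate-answer prompt after Don't Know and offer Not Applicable beside a valid 0, so some recent-partner data can go missing or become ambiguous

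*Protocol*

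**What the plan says.** Section 4.8.1 of the protocol (HIV Power Calculations) bases the HIV sample size on multiple sexual partners, defined as "more than one partner at the same time, or at least two partners in the previous year". Number of recent partners is also a hypothesised predictor in objectives 1a and 1b (Section 4, and again in Section 4.9).

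Appendix 7, Section F collects the recent counts.

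- **F1** asks "How many people did you have sex with in the 12 months before your blood donation". It is a two-digit field with codes 97 (Don't Know), 98 (Refuse) and 99 (Not Applicable). Its only routing rule is "If F1 is equal to 0, then skip to instruction Section H".
- **F2** asks the same for 6 months, with the same codes. A hidden note says "This is the seed number for the social matrix (0 up to 5 partners in last six months" and adds that "persons with more than 5 partners will only be asked about 5 partners".

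Section E collects the lifetime counts E2a and E3a. There, a Don't Know is followed by E2a.1 or E3a.1: "If you Don't Know, can you give an approximate answer". The lead-in to Section E also says "If you cannot remember the precise answers below, please provide your best estimates". E2a and E3a carry a Not Applicable code as well. The rule that takes never-sexual men past the partner sections is "If E2a is equal to 0 and E3a is equal to 0 and B1 is equal to 1, then skip to Section H", with a parallel rule for women.

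**The concern.** The sponsor foresaw that donors may not know an exact partner count and built a remedy, but only for lifetime totals. The recent counts carry the study's hypotheses, and they lack it. An uncertain answer is plausibly more common among donors with several partners, who matter most for this exposure.

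More than one variable depends on these two items. F2 opens the partner blocks, and these supply the data for three further hypothesised predictors in objective 1a: recent change of partner (F5), older male/younger female partnership (F4) and unprotected receptive anal sex (F23, F24). Concurrency, the other part of the power exposure, would mostly have to come from the relationship dates in the same blocks (F5, F6b).

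At the low end, Not Applicable competes with 0 as the way to say none. Only 0 is recognised by the routing, so one true state can be stored under two codes and follow two paths.

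**Working it through.** The documents give no rate of Don't Know or Not Applicable answers, so this check compares items and traces answer patterns. The detectable odds ratios in Table 8 are not in question here.

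**Step 1. Items side by side**

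| Item | Window | Follow-up after Don't Know | Not Applicable offered | Skip on |
|---|---|---|---|---|
| E2a, E3a | lifetime | yes (E2a.1, E3a.1) | yes | both equal to 0 |
| F1 | 12 months | none | yes | 0 |
| F2 | 6 months | none | yes | none stated |

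The best-estimate invitation stands in the Section E lead-in. The Section F lead-in does not repeat it. It asks for accuracy and tells donors that some questions may not apply to them.

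**Step 2. Answer patterns for the previous-year exposure (two or more partners) and the partner blocks**

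| F1 | F2 | Previous-year exposure | Partner blocks |
|---|---|---|---|
| 7 | 6 | exposed, count intact | five |
| 97 | 3 | exposed, since 3 in 6 months implies at least 3 in 12 | three |
| 97 | 1 | not determined | one |
| 3 | 97 | exposed | no rule |
| 97 | 97 | no value | no rule |
| 99 | any | ambiguous at F1; the zero skip does not fire | depends on F2 |

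The first row shows that the cap limits partner detail and leaves the count alone. The second shows that F2 can rescue some F1 Don't Know answers. The third and fifth are the donors whom a prompt at F1 would help. The fourth and fifth are those whose partner-level data depend on a prompt at F2.

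**Step 3. Donors who never had sex**

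The skip before Section F needs E2a = 0 and E3a = 0 together. A man who enters 0 for women and Not Applicable for men fails it, is asked F1, and may choose Not Applicable again. A man who enters 0 twice never sees F1, and his recent count is zero by structure. Both are in the same true state.

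**Step 4. What loss would do to the odds ratio**

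Let a and b be the fractions lost among exposed and unexposed cases, and c and d the same among controls. Then

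complete-case OR = true OR × [(1 − a)/(1 − b)] ÷ [(1 − c)/(1 − d)].

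If cases and controls lose data alike (a = c, b = d), the factor is 1: the odds ratio is unchanged and only precision falls. If loss differs by case status, the odds ratio can move either way. The documents give none of a, b, c or d, so neither direction nor size can be stated.

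**The case against.** The strongest case against is that little is lost in practice.

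- The exposure is a cut at two or more, and F1 accepts large counts. A donor with many partners who gives any number is classified correctly. This stands. A reader might infer from the cap of five that the exposure is truncated at the top, or lost at both extremes. The text does not support that, because the cap governs how many partners are described and 0 is an accepted answer at the other end.
- A Don't Know at F1 still leads to F2, and two or more there settles the exposure. This stands for some donors, but not for those who answer Don't Know again or report fewer than two at F2.
- Code 99 is distinct from 97 and 98, and can be checked against E2a, E3a and the age-at-first-sex items. Section 4.9 plans checks of coding and consistency, followed by weighting or multiple imputation. This stands in part: many 99s could be recoded. A Don't Know that depends on the count itself is different. Weighting or imputation can repair it only under assumptions the data cannot test, and a partner block that was never opened cannot be reliably rebuilt.
- A reader might also infer that codes 97 to 99 are fed into the seed as numbers above five. The protocol does not say so; it only lacks a rule. Taken alone, that gap is a programming detail that ACASI development and pilot testing would normally settle.

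**Conclusion.** The point holds as a minor, avoidable weakness of the instrument. F1 and F2 lack the prompt given to the lifetime counts, and four count items offer Not Applicable beside a valid 0 that alone triggers the skips. As a result, some donors may have no recent count, some may lack partner-level data, and zeros may be split over two codes, with some never-sexual donors routed into Section F.

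It is tempting to convert this into lost power or a shifted odds ratio. That would need the share of donors who never had sex, the share choosing Not Applicable and the Don't Know rate, each by case status. None is in the protocol, so no figure should be attached. The conclusion rests on the questionnaire text and on one plausible but unverified assumption: that uncertainty about a recent count is more common among donors with several partners.

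**What to change.** 1. Add F1.1 and F2.1 after Don't Know, in the wording already used for E2a.1: "If you Don't Know, can you give an approximate answer". For F1, ask at least whether it was two or more, since that settles the previous-year exposure.
2. Remove Not Applicable from E2a, E3a, F1 and F2, and instruct that none is entered as 0. The age-at-first-sex items can keep it.
3. State that the matrix seed is min(F2 or F2.1, 5) for real counts only, so that 97 to 99 are never read as numbers. If the count remains unknown (not refused) and F1 is not 0, ask about the most recent partner within the 6-month window, if there was one.

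The cost is two short screens shown only after Don't Know, one deleted response code on four items, one routing rule, and some rounding error in approximate counts. The change is best made before OMB clearance, for which Section 4.6 allows up to nine months, because an answer that was never requested cannot be added later.

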#### **4. Objectives**

1a: To identify the demographic and behavioural risk factors associated with incident HIV infection (based on “NAT yield” or LAg Avidity testing) among blood donors in South Africa.

Hypotheses: 1) The risk factors for incident HIV in blood donors in South Africa will include a recent change in sexual partner, older male/younger female sexual partnership, a greater number of recent sexual partners, unprotected receptive anal intercourse, and lower socioeconomic status.

1b: To identify the demographic and behavioural risk factors associated with incident HBV infection among blood donors in South Africa identified as “NAT-yields” or concordant serology and NAT positive and anti-HBc negative.

Hypotheses: 1) The risk factors for incident HBV in blood donors in South Africa will include greater number of recent sexual partners, recent scarification/tattoo/body markings, and history of personal contact with an HBV-infected person.

2a: To determine HIV subtype and drug resistance profiles among HIV positive donors with recently acquired infection based on year of donation and site of collection, and examine findings with donor demographics and risk behaviors derived in Objective 1.

Hypotheses: 1) The proportion of donors identified with incident HIV infection containing drug resistance mutations will be positively related to the proportion of HIV-positive individuals receiving anti-retroviral therapy at a population-level in South Africa

2b: To determine HBV genotype profiles among HBV positive donors with recently acquired infection based on year of donation and site of collection, and correlate findings with donor demographics and risk behaviors derived in Objective 1

Hypotheses: 1) Incident HBV infections will show differences in genotypes with genotype E increasing when compared to public health data on prevalent infections.

3: To prospectively characterize the virology, immunology and natural history of incident HIV infection among a cohort of recently infected blood donors and a small group of elite controllers in South Africa.

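### The partner matrix dates the relationship rather than first and last sex, which leaves recent partner change and separately analysed concurrency open to error that cannot be repaired afterwards

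*Protocol*

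**What the plan says.** Protocol section 4 (Objectives), hypothesis 1a, names "a recent change in sexual partner" first among the expected risk factors for incident HIV. Section 4.9 lists it first among the predictors. No time window or coding rule is given.

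Protocol Appendix 7, Section F, collects partner-level data on up to five people with whom the donor had sex in the 6 months before donation. For each partner:

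- F5 asks "When did your relationship with partner 1 start", as month and year.
- F6a asks "Are you currently have sex with partner 1". If the answer is yes, F6b is skipped.
- F6b asks "When did your relationship with partner 1 end", as month and year.
- F5, F6a and F6b all accept 99 (Not Applicable) besides Don't Know and Refuse to Answer. Nothing says when 99 applies.
- F7 then classifies the partner as primary, regular, casual, one-time, anonymous or sex worker. All types receive the same date items.

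The questionnaire defines sex in Sections E and G. It does not define relationship.

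The HIV power calculation in section 4.8.1 uses a different exposure, multiple partners, described as "more than one partner at the same time, or at least two partners in the previous year".

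**The concern.** Whether a partner is new depends on when sex with that partner began. Whether two partnerships overlap depends on first and last sex with each. The matrix asks instead for the start and end of a relationship, and it gates the end date with a question about sex. The two can diverge in either direction: a couple may be together for some time before first sex, or may have sex for some time before either calls it a relationship.

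At stake is the measurement of the first exposure named in hypothesis 1a, and of concurrency if it is analysed separately. Dates that were never collected cannot be restored by any analysis plan, so this has to be settled in the instrument.

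**Working it through.** The main check sets the items side by side.

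**1. What the other items can supply.**

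| Item | What it gives | Does it date first or last sex with a partner? |
|---|---|---|
| F1 | Number of sex partners in 12 months | No |
| F2 | Number of sex partners in 6 months; seeds the matrix | No |
| Matrix instruction | Partners listed from most recent sex backwards | Gives order of last sex, no dates |
| F7 | Partner type | Only indirectly, for one-time partners |
| F17 to F25 | Number of acts per partner, by category | No |

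A donor with F1 = 1 and F2 = 1 may have a long-standing partner or a new one. A donor with F2 = 2 may have had two successive partners or two overlapping ones.

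**2. New or not new.** The protocol sets no window. Take 6 months, the questionnaire's own recall interval, for illustration.

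- *Relationship began before the window, first sex inside it.* F5 records an old partner; by sex the partner is new (lost sensitivity).
- *First sex before the window, relationship said to begin inside it.* F5 records a new partner; by sex the partner is old (lost specificity).
- *F5 = 99 for a casual partner or a repeat sex-worker contact.* Newness is unknown.
- *F7 = 4,* "One time partner - Had sex only once". The partner is in the matrix only because of sex in the 6 months before donation. With a single act, that act lies in the window. The partner is new whatever F5 says; only the month, and so order or overlap, is lost.

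**3. The F6a/F6b route.** A donor who has stopped having sex with a spouse but is still married answers No to F6a and goes to F6b, where no true end date exists. The date of last sex, which overlap needs, is not asked.

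**4. Timing of F6a.** It refers to the interview. Under section 4.2.2, controls are invited to the questionnaire after donating. Cases complete it at a later return visit, at which they are told they are likely to be HIV or HBV positive. A case whose sexual activity stopped after the donation can therefore be routed differently from a control with the same history up to donation.

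**5. The power exposure.** Let A be two partners at the same time within the previous year, and B at least two partners in that year. A implies B, so A or B equals B, which is F1 ≥ 2. F5 and F6b are not used. Table 8 belongs to this exposure. Its middle row gives (0.30/0.70)/(0.20/0.80) = 1.71 against the stated 1.74; that small gap is not at issue here.

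**6. Size, for orientation only.** The protocol gives neither a prevalence for partner change nor any error rate. Suppose an exposure of 20% in controls and 30% in cases (proportions borrowed from Table 8), 300 cases and 900 controls, independent sampling, two-sided 0.05, and the same error in both groups. Observed prevalence is p × Se + (1 − p) × (1 − Sp).

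| Assumed Se / Sp | Controls | Cases | OR | Power |
|---|---|---|---|---|
| 1.0 / 1.0 | 0.200 | 0.300 | 1.71 | 0.94 |
| 0.9 / 1.0 | 0.180 | 0.270 | 1.68 | 0.91 |
| 0.8 / 0.95 | 0.200 | 0.275 | 1.52 | 0.77 |
| 0.7 / 0.9 | 0.220 | 0.280 | 1.38 | 0.56 |

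The spread runs from trivial to serious, depending wholly on the assumed Se and Sp. It shows only that the point cannot be sized from the protocol.

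**The case against.** The case for leaving the items alone has several parts.

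- *Context.* The section concerns sexual experience, and F6b follows directly from a question about sex, so many donors will read relationship as the sexual one. This is fair, and it means that error is a risk rather than a demonstrated fact. But the word is undefined and the same matrix could ask directly: F15 already speaks of becoming sexually involved.
- *Other timing information.* Partners are listed by recency of sex and all fall within 6 months. This orders last sex but does not date first sex, so newness and overlap stay undetermined.
- *The separated spouse.* F6a = No records that sex has stopped, so false concurrency arises only if the analyst ignores it. Correct, but when sex stopped is still unknown.
- *Derivation rules.* The window for recent change and the handling of code 99 may properly sit in an analysis plan. That stands, and their absence is not the point here. A plan cannot supply the missing dates.
- *Dropping code 99 does not guarantee dates.* True: Don't Know and Refuse to Answer remain, and items may be skipped. It only removes a code whose meaning is unclear once the item is about sex that is known to have occurred.

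Two stronger readings are tempting, and the protocol does not support them. A reader might infer that the power exposure is misclassified because its definition mentions simultaneous partners; F1 ≥ 2 captures it in full. A reader might also infer that the error falls mainly on the riskiest partner types; one-time partners are recoverable as new from F7 and the matrix window, and the description of anonymous partners points the same way.

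**Conclusion.** The point holds in a limited form. For primary, regular, casual and repeat sex-worker partners, F5 alone decides whether the partner is new, and it may differ from first sex or be missing. F6a and F6b mix sex with relationship, and they tie the routing to the interview rather than the donation. Recent change in sexual partner and concurrency as a separate variable are therefore at risk of measurement error that cannot be recovered.

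The size is unknown. The illustrative odds ratios and power values rest on assumed sensitivity and specificity, on proportions borrowed from an exposure that is not affected, and on ignoring clustering; they are not an estimate for this study. Attenuation toward 1 also presumes equal error in cases and controls, which the different interview timing does not guarantee. Table 8 and the sample size are untouched. This is an inexpensive improvement to the instrument and does not threaten the design.

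**What to change.** In all five partner loops of Appendix 7, Section F:

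1. Reword F5 to ask the month and year of first sex with the partner.
2. Replace F6a and F6b with one item asking the month and year of last sex with the partner before the index donation. This puts cases and controls on the same reference date.
3. Remove Not Applicable from these items and keep Don't Know and Refuse to Answer.

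The cost is two reworded items and one deleted item per loop, with the matching change in the computer-assisted interview. It is smallest before the instrument goes for the OMB clearance described in section 4.6. There is a small downside: relationship length is no longer asked directly, and first sex may be harder to date for long-term partners.
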